1.3 Exploratory Aims

- 1.3.1 To determine the EFS, OS, and DoR of children with TRK fusion solid tumors other than IFS treated with adjuvant larotrectinib following upfront surgery with positive margins after neoadjuvant larotrectinib.
- 1.3.2 To determine the EFS, OS, and DoR of children with TRK fusion solid tumors who experience a complete response to larotrectinib and subsequently discontinue larotrectinib therapy
- 1.3.3 To determine the remission induction rate for patients with recurrent/refractory TRK fusion leukemia when treated with larotrectinib.
- 1.3.4 To evaluate the surgical morbidity and extent of resection of initially unresectable tumors in patients with TRK fusion solid tumors who undergo surgical resection following neoadjuvant larotrectinib.
- 1.3.5 To evaluate mechanisms of response and resistance to larotrectinib in children with TRK fusion cancers.
- 1.3.6 To evaluate the morphologic features of TRK fusion solid tumors at time of initial

biopsy to further define criteria for pathologic diagnosis of these tumors.

- 1.3.7 To evaluate immunohistochemistry for pan-TRK as a screening method for TRK fusion tumors and in resection specimens following neoadjuvant treatment with larotrectinib.
- 1.3.8 To evaluate the histologic response to larotrectinib in resection specimens following neoadjuvant treatment.
- 1.3.9 To evaluate circulating tumor DNA for the detection of the emergence of resistance mutations and recurrence in patients with TRK fusion solid tumors treated with larotrectinib.
- 1.3.10 To evaluate the ratio of CSF to concurrent plasma concentrations of larotrectinib in patients with leukemia.
- 1.3.11 To evaluate the change in neurocognitive/behavioral functioning over time between baseline and 5 years post-diagnosis of patients treated on this protocol using parent-reported adaptive functioning (ABAS-III General Adaptive Composite), executive function (BRIEF-P or BRIEF-2 Global Executive Composite Score), psychosocial functioning (BASC-3 Internalizing, Externalizing and Behavioral Symptoms Indices) and quality of life (PedsQL Total score).

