Patients who have stable disease or a partial response and do not have localized, resectable disease will continue on larotrectinib therapy for up to 26 cycles. This group includes all patients who enroll with metastatic disease and do not achieve a complete response. After 26 cycles, such patients will have completed planned therapy and enter Follow-up ([Section 7.2](#)). Patients who are continuing to experience benefit from larotrectinib at the completion of 26 cycles of therapy and for whom their treating physician determines it is not in their best interest to discontinue therapy and be observed may be able to continue treatment utilizing commercial supply (if approved by the local health authority), an expanded access protocol, or single patient protocol as appropriate and available at that time.

4.1.3.3 Patients who Achieve a Complete Response:

Patients who achieve a complete response from only larotrectinib therapy (without surgery) will receive 6 additional cycles of therapy after achieving CR or a minimum of 12 cycles of therapy (whichever occurs later). Such patients will subsequently have completed planned therapy and enter Follow-up ([Section 7.2](#)).

4.1.3.4 Patients with Progressive Disease:

Patients who have progressive disease at any time will be taken off therapy.

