9.3 Methods of Analysis

Response criteria are described in [Section 10.2](#). A responder is defined as a patient who achieves a best response (as defined in [Section 10.3.4](#)) of PR or CR on the study. Response rates will be calculated as the percent of evaluable patients who are responders, and confidence intervals will be constructed accounting for the two-stage design.

Toxicity tables will be constructed to summarize the observed incidence by type of toxicity and grade. A patient will be counted only once for a given toxicity for the worst grade of that toxicity reported for that patient. Toxicity information recorded will include the type, severity, time of onset, time of resolution, and the attribution(s) to the study regimen.

Time-to-event analyses (time to progression, progression-free survival, overall survival, and duration of response) will be computed one year after the last enrollment in a stratum. Duration of response will be defined among patients with a confirmed best response of either PR and CR, and will be defined as the time from the first observation of either PR or CR until either the first observation of PD (event) or last known observation of the patient (censored observation).

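### Duration of response (DoR) for exploratory aims 1.3.1 and 1.3.2 starts before the event that forms each group, which builds in event-free time; EFS and OS have no stated origin

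*Combined protocol and SAP*

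**What the plan says.** Section 1.3 lists two exploratory aims that each name EFS, OS and DoR. Aim 1.3.1 covers children with tumors other than infantile fibrosarcoma "treated with adjuvant larotrectinib following upfront surgery with positive margins after neoadjuvant larotrectinib". Aim 1.3.2 covers children "who experience a complete response to larotrectinib and subsequently discontinue larotrectinib therapy".

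Section 9.3 is the only place that defines a clock: "Duration of response will be defined among patients with a confirmed best response of either PR and CR", and it "will be defined as the time from the first observation of either PR or CR until either the first observation of PD (event"), with censoring at the last known observation. The analyses it covers are listed as "Time-to-event analyses (time to progression, progression-free survival, overall survival, and duration of response"); EFS is not among them, and OS, PFS and time to progression get no origin. All of them "will be computed one year after the last enrollment in a stratum".

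The treatment rules decide who can enter each group. Under 4.1.3.3, patients in CR "will receive 6 additional cycles of therapy after achieving CR or a minimum of 12 cycles of therapy", whichever is later, up to the overall limit of 26 cycles. Under 4.1.3.1, resection follows at least 6 cycles, plus up to one more during surgical planning. Under 4.1.3.4, progression at any time ends therapy.

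**The concern.** Membership of either group is known only at a later date: the day of surgery, or the day larotrectinib stops. A child who progresses before that date is taken off therapy, so does not reach the planned stop or go on to adjuvant drug after protocol surgery. Everyone in the group has therefore survived progression-free up to the qualifying event. Starting DoR at first response counts that stretch as response time although no member could have failed in it. This is immortal time bias.

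The aims ask how long control lasts after stopping in CR, and after a positive-margin resection followed by more drug. DoR from first response mixes that period with the time before it. In aim 1.3.1 the clock also runs straight through the operation that removed the responding tumor. A long DoR could then be read as support for stopping that the data do not give.

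**Working it through.** The plan states no sample size, event count or rate for these two aims, so there is no figure of its own to reproduce. The lead times below follow from its schedule.

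**Inputs.** Cycle length is 28 days and the maximum is 26 cycles (4.1.3). Scans are done after Cycles 2, 4, 6, 9, 12, 16, 20 and 24 (7.1). Planned stop after CR: 4.1.3.3. Earliest surgery: 4.1.3.1. Confirmation of response needs a gap of at least 3 weeks (10.4). One month = 365.25/12 days.

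**Aim 1.3.2, read as planned stops in CR.** Stop cycle = min(26, max(12, CR cycle + 6)). Lead = 28 × (stop cycle − CR cycle).

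| First CR seen after cycle | Stop after cycle | Lead (days) | Lead (months) |
|---|---|---|---|
| 2 | 12 | 280 | 9.2 |
| 4 | 12 | 224 | 7.4 |
| 6 | 12 | 168 | 5.5 |
| 9, 12, 16, 20 | 15, 18, 22, 26 | 168 | 5.5 |
| 24 | 26 (limit) | at most 56 | 1.8 |

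The stated clock starts at the first PR or CR, so an earlier PR adds to this. PR after Cycle 2 and CR after Cycle 9 gives a stop after Cycle 15 and a lead of 28 × 13 = 364 days, almost the whole first year.

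**Aim 1.3.1.** Lead = 28 × (surgery cycle − cycle of first PR), for surgery after Cycle 6 or 7.

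- PR after Cycle 2: 112 to 140 days (3.7 to 4.6 months).
- PR after Cycle 4: 56 to 84 days (1.8 to 2.8 months).
- PR after Cycle 6: 0 to 28 days (0 to 0.9 month); the floor is about 21 days if the response is confirmed before surgery.

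Later surgery lengthens each of these. Patients with stable disease can also reach surgery under 4.1.3.1, and they have no DoR at all.

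**Illustration for aim 1.3.2.** The documents give no relapse rate after stopping. Assume a constant hazard after the stop and a proportion S free of relapse 12 months after it. With lead g days, 12-month DoR from first CR is S^(1 − g/365.25).

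| S from stopping | g = 56 | g = 168 | g = 280 |
|---|---|---|---|
| 50% | 56% | 69% | 85% |
| 70% | 74% | 82% | 92% |
| 90% | 92% | 94% | 98% |

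For S = 70% and g = 168: 0.70^(1 − 0.460) = 0.70^0.540 = 0.82.

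**Follow-up at the planned cut.** The earliest planned CR stop is day 12 × 28 = 336. One year after enrollment, the last patient has 365 − 336 = 29 days after stopping, or 24 if therapy started on the latest permitted day (5 days after enrollment, 3.1.5). The first scheduled off-drug evaluation is at 3 months (7.2). With CR after Cycle 9 the stop falls on day 15 × 28 = 420, after the cut.

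**The case against.** The strongest reply is that 9.3 gives a general definition of DoR and never says that it will be applied unaltered to these two groups, which are exploratory and carry no hypothesis or decision rule. Visits after planned completion are already timed from discontinuation (7.2) and run to five years from entry, so outcomes after stopping can be reported without new data. This limits the weight of the point. It does not remove it, because both aims name DoR and the plan holds only one definition of it.

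Several stronger readings are tempting and are not supported:

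- *All three endpoints contain guaranteed time.* Only DoR has a stated clock. If EFS and OS were run from first dose, the lead would be at least 6 × 28 = 168 days for aim 1.3.1 and, for nearly all planned CR stops, at least 12 × 28 = 336 days for aim 1.3.2. That origin is an assumption; what the plan lacks is a definition.
- *No one in aim 1.3.2 could fail before stopping.* The aim speaks only of discontinuing after CR. Read literally, it could include a child who stopped because of progression or toxicity, and then no interval is guaranteed.
- *Every late CR carries 168 days.* The 26-cycle limit cuts this to at most 56 days for CR first seen after Cycle 24.
- *Aim 1.3.1 is affected to the same degree.* Its lead can be under one month.
- *82% to 92% against 70% is the bias in this trial.* The relapse rate is assumed, and the two figures answer different questions: 12 months from CR and 12 months from stopping.

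**Conclusion.** The point holds for DoR. Applied as written, the 9.3 clock includes event-free time that comes from how the groups are formed. In aim 1.3.2 this is 168 to 280 days from first CR for CR seen after Cycles 2 to 20, at most 56 days for CR first seen after Cycle 24, and more when a PR came first. It rests on reading the aim as planned stops while in CR. In aim 1.3.1 the lead is under 1 month to about 4.6 months for surgery after Cycle 6 or 7, and longer for later surgery. The lead times follow from the protocol schedule; the percentages depend on an assumed constant hazard and relapse rate.

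For EFS and OS the finding is narrower: no origin is stated, and EFS does not appear in 9.3. The one-year cut adds a separate problem, since the patients enrolled last would have little or no follow-up after the qualifying event. Both aims are exploratory and the primary response-rate decision does not depend on them, so this should be corrected before these aims are reported but is not critical to the trial.

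**What to change.** Add to 9.3:

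1. **Aim 1.3.2.** Define the group as patients who stop as planned while in CR. Judge CR at the last evaluation on or before the last dose, because 7.1 requires none at discontinuation. Measure time to progression, recurrence or death, and OS, from the last larotrectinib dose.
2. **Aim 1.3.1.** Measure the same endpoints from the resection date.
3. **DoR.** The aims name it, so it need not be dropped. If it is reported from first response, label it as descriptive and as including guaranteed event-free time, or use a landmark or left-truncated estimate.
4. **Selection.** List beside aim 1.3.2 the patients who reached CR but progressed before the planned stop.
5. **EFS.** State its events and origin.
6. **Data cut.** Report these two aims when patients have real follow-up after the qualifying event, rather than at one year after last enrollment.

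The cost is wording and time. Follow-up visits are already tied to discontinuation, doses are recorded in diaries, operative reports are collected, and follow-up runs to the fifth anniversary of enrollment. No treatment rule changes. The downsides are shorter reported durations and a later report for these two aims. Section 2.7.1 says that accrual is complete, so the change affects analysis and reporting only.

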4.3.2 Required Observations for Cycles 2+, Cohorts A & B

- a. Hx/Wt /Ht/BSA. Within 7 days prior to subsequent cycles and at the end of study treatment.
- b. Performance status. Prior to subsequent cycles.
- c. Physical exam (including VS and neurologic examination). Prior to subsequent cycles and at the end of study treatment.
- d. CBC/diff/platelets: Prior to subsequent cycles. If patients have Grade 4 neutropenia then CBCs should be checked every 3 to 4 days until recovery to Grade 3 or until meeting the criteria for dose limiting toxicity.
- e. Electrolytes including Ca⁺⁺. Prior to subsequent cycles.
- f. Creatinine, ALT, bilirubin. Prior to subsequent cycles.
- g. Disease evaluation. After cycles 2, 4, 6, 9, 12, 16, 20, and 24. If the institutional investigator determines that the patient has progressed based on clinical or laboratory evidence, he/she may opt not to confirm this finding radiographically. Please refer to [Section 10.4](#) for Confirmation of objective response by RECIST 1.1.
- h. Bone marrow evaluation. With Disease evaluation. Bone marrow aspirate and/or biopsy should only be performed on patients with solid tumors with bone marrow involvement at baseline. If the institutional investigator has determined the patient has progressed based on clinical or laboratory evidence, he/she may opt not to confirm this finding on marrow pathology.
- i. Circulating tumor DNA. On Day 1 of Cycle 2, at the end of cycle 6 (Day 1 of Cycle 7 or prior to local control), and at the time of progression. See [Section 7.3.2](#) for details.
- j. Tumor tissue submission. Submission of tumor tissue from any surgical resection or bone marrow evaluation for patients with involvement by tumor while on study is required. For patients who undergo resection of their tumor while on study, operative reports and hospital discharge summaries must be uploaded into RAVE following surgical resection. Submission of tumor tissue from any biopsy after progression is optional. See [Section 7.3.1](#) for details.
- k. Patient diary. Uploaded into RAVE at the end of each cycle. See [Appendix VII-A](#) and [Appendix VII-B](#) for details.
- l. Pregnancy test. Prior to subsequent cycles. Sexually active patients must use an acceptable method of birth control.

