³ Disease evaluation includes CT or MRI of all known sites of disease. For patients with solid tumors, disease evaluation will be performed after Cycles 2, 4, 6, 9, 12, 16, 20 and 24. For patients with leukemia, disease evaluation will occur after Cycles 1, 2, 4, 6, 9, 12, 16, 20, and 24. Please note that for solid tumor patients, if the institutional investigator determines that the patient has progressed based on clinical or laboratory evidence, he/she may opt not to confirm this finding radiographically. . Please refer to [Section 10.4](#) for Confirmation of objective response by RECIST 1.1. Patients who enter follow-up after completion of planned therapy per [Section 4.1](#) should follow the disease evaluation schedule defined in [Section 7.2](#) and do not require disease evaluation at the time of discontinuation of larotrectinib.

⁴ See [Section 7.3.2](#) for timing of circulating tumor DNA (ctDNA) studies. ctDNA will be obtained at enrollment, Day 15 of Cycle 1 of larotrectinib therapy, Day 1 of Cycle 2 of larotrectinib therapy, at the end of Cycle 6 of larotrectinib therapy (prior to Cycle 7 or local control), at the end of study treatment, and at the time of progression.

⁵ See [Section 7.3.1](#) for details regarding tumor tissue submission. If tissue blocks or slides are unavailable, the study chair must be notified prior to study enrollment.

⁶ Patient diary (see [Appendix VII-A](#) and [Appendix VII-B](#)) should be reviewed and uploaded into RAVE at the end of each cycle.

⁷ Bone marrow aspirate and/or biopsy only required in patients with leukemia or solid tumors with known bone marrow metastasis on the basis of history, symptoms, laboratory evaluation or other clinical data.

⁸ Bone marrow aspirate and/or biopsy should only be performed on patients with leukemia or solid tumors with bone marrow involvement at baseline. If the institutional investigator has determined the patient has progressed based on clinical or laboratory evidence, he/she may opt not to confirm this finding on marrow pathology.

⁹ Submission of tumor tissue from any surgical resection or bone marrow evaluation for patients with bone marrow involvement by tumor, including patients with leukemia, while on study is required. For patients who undergo resection of their tumor while on study, operative reports and hospital discharge summaries must be uploaded into RAVE following surgical resection.

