7.2 Follow-up

| STUDIES TO BE OBTAINED | While in Follow-up after Completion of Planned Therapy per Section 4.1 ¹ | While in Follow-up for Other Reasons ⁶ |
|---|---|---|
| History, including any anti-cancer therapy received | X ² | X |
| Physical exam with VS, including neurologic examination | X ² | X |
| Ht, Wt, BSA | X ² | X |
| Disease evaluation | X ² | X |
| Circulating tumor DNA | X ³ | |
| Tumor tissue submission | X ⁴ | X ⁴ |
| Neurocognitive assessments | X ⁵ | |

¹ Patients who have progressive disease while in Follow-up after completion of planned therapy will be subsequently monitored per the table for patients in Follow-up for other reasons.

² At 3, 6, 12, 18, 24, 30, 36, and 48 months after discontinuation of larotrectinib, and annually thereafter for up to 5 years from the date of study entry. Studies may be obtained \pm 14 days of the indicated timepoint.

- ³ See [Section 7.3.2](#) for timing of circulating tumor DNA (ctDNA) studies. For patients in Follow-up, ctDNA will be obtained at the time of progression.
- ⁴ Submission of tumor tissue from any biopsy after progression is optional.
- ⁵ See [Appendix XI](#). For patients in Follow-up, neurocognitive tests will be obtained 6 months (\pm 4 weeks) after enrollment, 12 months (\pm 4 weeks) after enrollment, 24 months (\pm 4 weeks) after enrollment, and 4-5 years after enrollment. Timing should be based on enrollment, regardless of whether the patient is receiving larotrectinib or is in Follow-up.
- ⁶ Follow-up for patients who discontinue therapy on this study for reasons other than completion of planned therapy ([Section 8.0](#)) is required at 30 days, 6 months, and 12 months from the last date of protocol therapy, and annually thereafter for up to five years from the date of study entry.

See COG Late Effects Guidelines for recommended post treatment Follow-up:
<http://www.survivorshipguidelines.org/>

Note: Follow-up data are expected to be submitted per the Case Report Forms (CRFs) schedule.

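### Section 9.3 censors duration of response at the last observation of the patient, not at the last assessment of disease status; any bias is upward, and small if the evaluation schedule is kept

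*Combined protocol and SAP*

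**What the plan says.** Section 9.3 defines duration of response, among patients with a confirmed best response, as "the time from the first observation of either PR or CR until either the first observation of PD (event"; without progression it runs to the "last known observation of the patient (censored observation". This is the only censoring date that Section 9.3 gives. Time to progression and progression-free survival are listed there without one. No section requires the date to be one on which disease was evaluated, and none gives a rule for missed evaluations. The time-to-event analyses "will be computed one year after the last enrollment in a stratum".

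Contact and disease evaluation are scheduled as follows for Cohorts A and B:

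- **On therapy, evaluation (Section 7.1):** "For patients with solid tumors, disease evaluation will be performed after Cycles 2, 4, 6, 9, 12, 16, 20 and 24".
- **On therapy, contact (Section 4.3.2):** "Physical exam (including VS and neurologic examination). Prior to subsequent cycles and at the end of study treatment".
- **At planned completion (Section 7.1, footnote 3):** these patients "do not require disease evaluation at the time of discontinuation of larotrectinib". The Section 7.1 table otherwise marks a disease evaluation at the end of study treatment.
- **Follow-up after planned therapy (Section 7.2):** history, examination and disease evaluation share one calendar, "At 3, 6, 12, 18, 24, 30, 36, and 48 months after discontinuation of larotrectinib, and annually thereafter for up to 5 years".
- **Follow-up for other reasons (Section 7.2):** this "is required at 30 days, 6 months, and 12 months from the last date of protocol therapy, and annually thereafter", and the table marks disease evaluation here too.
- **Questionnaires (Sections 3.1.7 and 7.2):** timed from enrollment and not tied to disease evaluation.

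Sections 4.3.2, 7.1 and 8.1 also allow progression to be declared on clinical or laboratory evidence without imaging.

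**The concern.** Progression can enter the data only when someone assesses the disease. If the censoring date is any later contact, the time between the last assessment and that contact is counted as continued response although disease status was not established. The patient then stays in the denominator when another child's progression is recorded.

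Duration of response is a secondary aim for Cohorts A and B (Sections 1.2.1 and 1.2.2). Under Section 8.1, children removed from therapy for refusal, non-compliance or physician decision are still followed, with data required unless consent is withdrawn. These are plausible patients for imaging to lapse while contact continues. The error would favor the drug, and it would be hard to see in cohorts this small.

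**Working it through.** **1. Plan's own figure.** The plan gives no event count, precision or power for duration of response, so there is nothing to reproduce on this point. As a background check, exact enumeration of the two-stage design returns its stated figures: type I error 0.0905, power 0.9040, early termination 0.5174, expected sample size 14.8.

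**2. Direction.** The estimate is S(t) = ∏(1 − d/n) over progression times. The times and the counts d do not depend on the censoring rule. Later censoring makes each n equal or larger, so each factor is equal or higher. Illustration with assumed numbers: 8 patients at risk, 2 of them without current disease status, one progression. Last-contact censoring gives 7/8 = 87.5%; removing the 2 gives 5/6 = 83.3%.

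**3. Gap if the schedule is kept.** Cycles are 4 weeks, so evaluations fall at weeks 8, 16, 24, 36, 48, 64, 80 and 96, with gaps of 8 to 16 weeks. The last cycle visit before the next evaluation can be at most 16 − 4 = 12 weeks after the previous one. A patient finishing 26 cycles is evaluated at week 96 and completes therapy at week 104. The next evaluation is 3 months later, at about week 117. In follow-up, scheduled visits include an evaluation, so the scheduled gap is zero apart from questionnaires.

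**4. Size.** Simulation of 30,000 virtual responders per scenario, with each patient censored both ways.

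Inputs from the documents:
- the Section 7.1 and 7.2 calendars;
- about 2.6 years of accrual (21 patients at 8 per year, Section 9.1) plus one year;
- 71% of responses ongoing at 12 months (Section 2.3.2, relapsed/refractory setting).

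Assumptions:
- exponential duration; 12-month rates of 85% and 93% as alternatives;
- first response at cycle 2, 4 or 6 in 70, 20 and 10%;
- therapy ending at cycle 7, 12 or 26 in 30, 20 and 50%;
- progression found only on scans;
- a stated share whose scans stop while contact continues.

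Kaplan-Meier estimate at 24 months (%):

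| True 12-month rate | Share stopping scans | Last contact | Last evaluation | Difference (points) |
|---|---|---|---|---|
| 71% | 0 | 53.58 | 53.04 | 0.54 |
| 71% | 10% | 55.23 | 52.38 | 2.85 |
| 71% | 20% | 57.14 | 51.89 | 5.25 |
| 71% | 30% | 59.66 | 52.20 | 7.46 |
| 85% | 0 | 73.98 | 73.62 | 0.36 |
| 85% | 10% | 75.84 | 74.16 | 1.68 |
| 85% | 20% | 76.67 | 73.59 | 3.08 |
| 85% | 30% | 78.16 | 73.78 | 4.38 |
| 93% | 0 | 87.62 | 87.42 | 0.20 |
| 93% | 10% | 88.18 | 87.29 | 0.89 |
| 93% | 20% | 88.86 | 87.33 | 1.53 |
| 93% | 30% | 89.35 | 87.13 | 2.22 |

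At 12 months, with the 71% rate, the four differences are 0.14, 0.88, 1.65 and 2.42 points. With the schedule kept, both columns exceed the true 24-month rates (0.71² = 50.4%, 0.85² = 72.3%, 0.93² = 86.5%) because progression is dated at the next scan. That excess is not caused by the censoring rule.

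A separate simulation with 20 responders and a true 24-month rate of 75% gives 0.3 to 0.4 points on schedule, about 1.3 points if 10% stop scanning, and 2.2 points if 20% do.

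**5. Precision.** 85% of 21 is about 18 responders. For a 75% rate the standard error is √(0.75 × 0.25 / 18) = 0.102, about 10 points.

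**6. Clinical detection of progression.** Take the 71% rate and let half of patients have progression detectable at clinic visits. On schedule, last-contact and last-scan censoring give 52.60% and 51.97%, a difference of 0.63 points. If 20% stop scanning, they give 54.09% and 49.63%, a difference of 4.46 points, against a true 50.4%. Scan-only censoring then falls below the truth. In the 75% simulation, with all progression clinically detectable and 20% stopping scans, it gives about 74%.

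**The case against.** The strongest reply is that the written schedule leaves the rule little room to act. Section 7.2 places disease evaluation on the same dates as history and examination in both follow-up columns. On therapy the last visit is never more than 12 weeks past an evaluation. The exemption from a scan at discontinuation covers planned completion only. This stands, and it is why the on-schedule effect is a fraction of a point.

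A reader might infer that duration of response is materially overstated under this plan. The documents do not support that. One can obtain about 1.2 points (for example 76.6% against 75.4%) by assuming contact without evaluation within 90 days of the data cut for off-therapy patients, but apart from questionnaires no schedule in the protocol creates such contact. Nor does any section say how many patients will stop evaluations while staying reachable.

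Second, a clinic visit carries disease information, because progression may be called without imaging. This also stands. It reduces the problem without removing it, and it rules out the tempting remedy of censoring at the last scan. That remedy would count clinical progressions as events while discarding clinical assessments that found none.

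Third, the same sentence of Section 9.3 uses the word observation for disease status, so the censoring date might mean the last disease observation. That reading is possible, but a phrase attached to the patient reads more naturally as last contact. If two analysts can differ, the term needs defining in any case.

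**Conclusion.** The point holds as a flaw in a stated rule, of minor weight. The direction is certain: if the rule has any effect, it raises the estimate. At 24 months the size is about 0.2 to 0.6 points when evaluations are kept. If 10 to 30% of patients stop evaluations but remain in contact, it is roughly 1 to 2 points with durable responses and up to about 7.5 points at the 71% rate. The 10 to 30% range, the exponential form and the mix of stopping times are assumptions.

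Against a standard error of about 10 points, most of these shifts would not change how the result reads. Duration of response is secondary, and the two-stage decision in Section 9.2 does not use it. The case for changing the rule is that the error runs one way, favors the drug and is avoidable.

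**What to change.** In Section 9.3, replace the censoring date with: *the last disease evaluation (imaging, or a documented clinical assessment of disease status of the kind that can establish PD) showing no progression*. State the same date for time to progression and progression-free survival; this is new text, since no rule exists there to amend. Report censoring at last contact as a sensitivity analysis.

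The cost is a few lines of text and no new visits or scans. Evaluation dates are already collected; clinical assessments count only where disease status was documented. Some censored patients will contribute slightly shorter follow-up, and the estimate may be slightly less favorable.

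Section 2.7.1 reports that accrual is complete and activity has been shown, so a change now could be called post hoc. Giving both results answers that. Follow-up runs to five years from enrollment, so later analyses can still use the corrected date.
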